3.1 Reporting of Participant Recruitment and Accrual

Sites will enter all recruitment activity into the REDCap database, from which the weekly recruitment and accrual report will be generated. This includes information on reasons for ineligibility of subjects. The following reports will be produced by Clinical Data Management (CDM) staff in the DCC on Tuesday mornings, both overall and by clinical center (see Appendix B, Table 3 for example):

- Number of infants screened
- Number of infants ineligible by reason
- Number of infants randomized
- Number of infants randomized versus established accrual targets
- Number of infants completing each post-delivery evaluation

Approximately every 3–4 months to correspond to full meetings of the SAIL Steering Committee, the staff biostatistician at BAC (Biostatistics Analysis Center) will produce a chart to display the cumulative number of infants successfully randomized at each site as compared to the targeted number, and a graph of overall cumulative accrual to date versus the targeted accrual based on the accrual goals. Reasons for withdrawal from follow-up and time to withdrawal will also be presented as data become available.

3.2 Data Quality and Monitoring Reports

CDM staff will produce the following reports to monitor overall data quality. These reports will be produced approximately every 3–4 months to correspond to full meetings of the SAIL Steering Committee. These reports will include, but are not limited to:

- Missing post-delivery data
- Missing forms
- Missing values
- Query rates
- Timely entry and verification

Additional monitoring reports that may be produced by CDM staff include incorrect opening of randomization envelopes, and query status updates.

3.3 Demographics and Other Baseline Data

The staff biostatistician will prepare reports summarizing the distributions of demographic and clinical characteristics (Appendix B, Tables 1-2), both overall and by clinical center. These will be prepared approximately every 3–4 months to correspond to full meetings of the SAIL Steering Committee.

3.4 Adverse Events

3.4.1 Serious Adverse Events

The serious adverse event (SAE) definitions are given in Protocol Section 9.2.2. These will include, for example:

- Death within the first 48 hours post delivery
- Pneumothorax, pulmonary interstitial emphysema (PIE) and pneumopericardium determined by radiographic evidence within the first 10 days of life
- Grade 3 or 4 IVH determined by head ultrasound findings within the first 10 days of life

Based on the premature infant population studied, the SAE categories of events that result in congenital anomaly/birth defect or require intervention to prevent permanent impairment or damage (devices) do not apply when defining events.

Serious adverse events (SAEs), regardless of whether they are unexpected or considered to be associated with the study, will be communicated immediately upon discovery of the event, by either telephone or fax. Reporting requirements are provided in the protocol and additional details will be provided in the Manual of Procedures (MOP) for the trial.

A description of all serious adverse events to date, without any intervention identifiers, will be presented at each meeting of the Steering Committee. This list will also be provided to the DSMC. The DSMC will ultimately adjudicate whether the reported adverse event is in fact an

adverse event, and a serious AE, if the SAE could be attributed to the intervention, and unblind the intervention identifiers if they deem it necessary.

3.4.2 Other Adverse Events

For Steering Committee Meetings, two types of summaries of adverse events will be produced. These data will also be provided to the DSMC.

- 1. A listing of all adverse events will be produced by the CDM staff in the DCC directly from the AE/SAE form in the REDCap database. This listing will include a description, date of onset, grade, and relationship to study intervention, and whether or not the event was serious.
- 2. The study biostatistician will produce summaries of the observed adverse events combined into categories, as needed, using SAS or another similar statistical tool. All the events, regardless of the relationship to the study intervention, will be included in these reports. These reports will combine data across all interventions and clinical sites. An example of the type of table which will be produced for safety analysis is shown in Appendix B.

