All of the standard reports described in the previous section will be provided to the DSMC with this analysis. Additional measures to be considered at the interim analysis include baseline clinical factors and adverse events. The study population for all of the analyses provided to the DSMC is the intent-to-treat population, including all participants and time points for which data have been entered and verified in the study database. A summary of the analyses to be included in the interim report is outlined below. Additional details of the statistical methods to be used are given in the next section regarding the final analysis.

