4.1 Blinding

The study will be blinded in treatment allocation; patients, parents and clinicians will be unblinded once treatment is assigned; and then blinded analyses. All analyses provided to the DSMC will be provided by intervention, but with the individual interventions identified only as A and B. The same code will be used for each intervention throughout the report. A sealed envelope with the codes for these interventions will be provided to the chair of the DSMC, to allow the DSMC to unblind these results if needed for safety reasons. These codes are also maintained by a member of the DCC who is not involved in the group trials and are not made

available to any other DCC members, including the statisticians. None of the personnel in the DCC, including the statisticians, will have access to these codes until the study has been completed, all data are entered and verified in the database, and the DSMC has approved unblinding of the intervention results.

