4.4 Evaluation of Safety

In addition to the standard reports, statistical analyses will be performed to compare adverse event rates between treatments. In particular, the rate of pneumothorax, pulmonary interstitial emphysema (PIE), and/or other serious adverse events (that have been adjudicated as potentially relating to the intervention; see Protocol section 8.2.2). In order to minimize the risk, this safety outcome will be compared between treatment arms after 1/6 (100 subjects) have completed the primary outcome, as well as at the two planned interim analyses for the primary outcome (1/3 and 2/3), since we would not expect any statistically significant differences in the rate after 100 subjects (with O'Brien-Fleming alpha 0.000002). Instead, we will look for a clinically meaningful double the risk in the intervention versus standard care arms. (Appendix B, Table 5)

All other adverse events not explicitly mentioned in the Protocol will also be included, regardless of their presumed relationship to the study intervention. Adverse events will be collapsed into groups based on body part depending on numbers seen. The proportion of subjects

with any adverse event will be compared between groups using an exact Mantel-Haenszel test. Comparisons between interventions will be primarily descriptive

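### SAP 3.4 sends the DSMC an arm-masked SAE list and pooled AE summaries, so the routine reports it specifies between the 100, 200 and 400 looks show no arm comparison; a closed A/B safety table is a cheap, modest improvement

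*SAP*

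**What the plan says.** **Routine reports.** SAP 3.4.1: "A description of all serious adverse events to date, without any intervention identifiers, will be presented at each meeting of the Steering Committee". It then adds: "This list will also be provided to the DSMC". SAP 3.4.2 describes an AE listing, whose stated fields do not include arm, and AE summaries, of which it says "These reports will combine data across all interventions and clinical sites". Both are made for Steering Committee meetings, and then: "These data will also be provided to the DSMC".

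**By-arm reports.** SAP 4.1, placed under Interim Analysis, says: "All analyses provided to the DSMC will be provided by intervention, but with the individual interventions identified only as A and B". SAP 4.4 schedules the between-arm safety comparison at 100 completers and at the two interim analyses (200 and 400), and SAP 5.3 repeats it at the end. Appendix A lists the same looks. At the 100-infant review the criterion is a doubling, not a p-value: "Instead, we will look for a clinically meaningful double the risk in the intervention versus standard care arms". Appendix B Table 5, the only adverse event table there, has columns A, B, Total and p-value.

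**Other DSMC information.** Protocol 7.3 gives the DSMC SAEs within 72 hours and AE reports monthly, in a format not stated. Protocol 9.2.5 allows expedited reviews. SAP 3.4.1 lets the DSMC unblind, and SAP 4.1 provides the means: "A sealed envelope with the codes for these interventions will be provided to the chair of the DSMC".

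**The concern.** Masking is right for the Steering Committee, which by Appendix A includes all site investigators. It is not needed for the DSMC, which already receives A/B output at the looks and whose task is to protect the infants.

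The harms that matter most here appear early: death within 48 hours, and air leak and grade 3-4 IVH within 10 days (Protocol 9.2.3). The by-arm looks are timed by 36 weeks PMA. Between looks, a DSMC relying on the SAP 3.4 reports sees totals only. To see an imbalance it must ask to unblind, or wait, and a pooled count seldom prompts the request. As an illustration, the 2013 trial tabulated in Protocol 8.2 had 2/124 against 8/126 pneumothoraces; pooled, that is 10/250 = 4.0%.

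**Working it through.** The plan gives no figure for this point, so there is none to reproduce. The check estimates how much earlier a routine A/B table would show an excess, and how often it would mislead.

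**Inputs**
- Accrual: 600 infants in 2.5 years (Protocol Summary), so 600/30 = 20 a month, or 20 × 12/52 = 4.615 a week. Uniform accrual and prompt data entry are assumed.
- Lag to 36 weeks PMA: 36 − 27 = 9 to 36 − 23 = 13 weeks, or 42-60 infants.
- Data at a look (SAP 4): "including all participants and time points for which data have been entered and verified in the study database". Early-harm data at the three looks therefore cover 142-160, 242-260 and 442-460 infants (71-80, 121-130 and 221-230 per arm).
- Gaps between looks: 100/20 = 5 months and 200/20 = 10 months. At 15-25 infants a month they are 6.7-4 and 13.3-8 months.
- Routine reports every 3-4 months: 3.5 × 20 = 70 infants, or 35 per arm. Two fit before the third look, at the second look +35 and +70 per arm.
- Event rates, from Protocol 8.2, for illustration: 1.6% vs 6.3% (2/124, 8/126); 5.1% doubled (control total 13/257); 7% doubled (7/103).
- Yardstick: SI events ≥ 2 × max(control events, 1). A variant also requires at least 5 SI events. SAP 4.4's doubling criterion belongs to its scheduled comparisons and is borrowed here only as a measure.
- Binomial counts, 200,000 simulated trials per scenario, twin clustering ignored.

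**Two A/B tables added between looks 2 and 3 (no event minimum)**

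| Control vs SI | Seen by look 2 | Seen by look 3, scheduled looks only | Seen before look 3, with added tables | Mean gain, SI infants |
|---|---|---|---|---|
| 1.6% vs 6.3% | 91% | 96% | 96% | 2.2-2.3 |
| 5.1% vs 10.2% | 65-66% | 72-73% | 73-74% | 3.5 |
| 7% vs 14% | 65% | 72-73% | 72-73% | 3.6 |

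The mean gain is over all trials that show the excess by look 3. About 5-7% of trials first show it at look 3. Of these, 71-81% would show it sooner, by about 50 infants per arm: 100/20 = 5 months. With the 5-event minimum, the mean gain at 1.6% vs 6.3% rises to about 7 SI infants.

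A second simulation (40,000 trials) added tables every 3.5 months after the first look, with the 5-event minimum, at 7% vs 14%. Of the signals found on schedule, 18% came earlier, by a median of 2.0 months (90th percentile 8.5). The chance of a signal by the third look rose from 0.72 to 0.76.

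**Tables from the start of the trial**
- No event minimum: mean gain of 29-45 SI infants. At 7% vs 14% it is 37-45, but with no true difference at 7% the same measure gives 29-37. Most of that gain is chance.
- At least 5 SI events: 16-37 SI infants, or 16 × 2/20 = 1.6 to 37 × 2/20 = 3.7 months. With no true difference at 7% it is still 12-18.

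**Chance two-fold splits against SI, no true difference**
- At 100 per arm (exact): 27% of rows at a 1.6% rate, 18% at 5.1%, 12% at 7%.
- At least one by look 3, scheduled looks only vs tables from the start: 42% vs 48-49% at 1.6%; 26-28% vs 42-43% at 5.1%; 19-21% vs 37% at 7%. With the 5-event minimum at 7%: about 18-19% vs 25%.

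Under the A/B code the DSMC sees splits in either direction, so it would notice more than these.

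**The case against.** **The SAP may already require A/B.** SAP 4.1 says all DSMC analyses, and SAP 3.4.2 points to Appendix B, whose adverse event table is by arm. But 4.1 sits under Interim Analysis and follows the description of the interim report, while the specific sentence in 3.4.2 says the routine summaries are pooled. The reader is left with two rules.

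**The text may be elsewhere.** Part of Protocol 7.3, a part of the SAP just before 3.1, and the Manual of Procedures could not be seen. This stands, and it limits the point to SAP 3.4 as written.

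**The DSMC has other tools.** A reader might infer that it is blind to harm between looks. The documents do not support that. It gets SAEs within 72 hours and monthly AE reports, its Chair adjudicates relatedness and holds the code, it can unblind, and under Protocol 7.3 it reviews the monitoring plans and so could ask for A/B tables. This lowers the priority. It does not replace a routine split, because none of these is stated to give one.

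**The gain is small and partly chance.** Correct, as shown above. The larger gains need tables before the first look, where small counts reach two-fold easily.

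**It is not free.** Three independent rows at 7% would show at least one chance split by look 3 in 1 − 0.81³ = 47% to 1 − 0.79³ = 51% of trials now, and in 1 − 0.63³ = 75% with tables from the start. DCC staff would also make comparative tables more often during unblinded enrolment. Reusing Table 5 unchanged would bring in p-values and a BPD row, which do not belong in a descriptive table between looks. These objections shape the fix; they do not remove the case for it.

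**Conclusion.** The point holds in a limited form. As written, the routine reports in SAP 3.4.1 and 3.4.2 give the DSMC no arm comparison between looks, and this is hard to square with SAP 4.1 and Appendix B Table 5. It is a cheap improvement of low to moderate priority.

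The benefit is timing. A reader might infer that a routine A/B table would catch many harms that the plan would miss. It would not: every look uses all entered data, and the third look reaches about the same detection as the two added tables. Nor do the documents show that SI raises air leak. Over the three trials in Protocol 8.2 the totals are (4+7+2)/(30+103+124) = 13/257 (5.1%) for control and (3+1+8)/(31+104+126) = 12/261 (4.6%) for SI.

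The sizes rest on accrual of 20 a month, prompt data entry, illustrative event rates, independent infants and a yardstick that the SAP does not apply between looks.

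**What to change.** Keep the pooled, unlabelled reports in SAP 3.4.1 and 3.4.2 for the Steering Committee, and add:

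> With each 3-4 monthly routine report the DSMC receives a closed, cumulative safety table split A/B under the Section 4.1 code. Rows: death within 48 hours; air leak (pneumothorax, PIE, pneumopericardium); IVH grade 3-4; other SAEs. The table shows counts and percentages only, with no p-values and no BPD row. It is not released to the Steering Committee. It is descriptive, spends no alpha and has no automatic trigger.

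State in SAP 4.1 that its coding covers these reports, and add a matching row to Appendix A.

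Cost: a few lines of text and a cut-down version of an existing table shell, made by the same DCC staff under the existing code. The real price is more frequent noisy counts, so the DSMC should read the table with judgement and be wary of small numbers, above all before the first look.

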4. INTERIM ANALYSIS

Since neonatal safety is a consideration in this study, we have chosen to use a group sequential design. Thus, in addition to the final analysis, there will be two interim statistical analyses during the course of this study. The purpose of the interim analyses will be to determine whether or not there is sufficient evidence of a difference between the treatment arms in the primary endpoint such that the trial should be discontinued prior to reaching the target accrual goal.

Interim analyses will be performed after approximately 1/3 (200 subjects) and 2/3 (400 subjects) of the total required patients have completed their primary outcome. An additional safety review will be undertaken after 1/6 (100 subjects) have completed their primary outcome. The results of the interim analyses will be presented to the SAIL Data Safety and Monitoring Committee (DSMC). The primary outcome for the interim analyses will be the comparison of death/BPD between the treatment arms. This comparison will be accomplished by means of a simple generalized estimating equation (GEE) model for death/BPD versus treatment (since adjustment for deliveries with multiple babies will be needed). An approximate O'Brien-Fleming boundary will be used at each interim look to calculate the nominal significance level to which interim p-values are compared (O'Brien PC, 1979). Using the O'Brien Fleming spending function, the three analyses (2 interim + final) should use the following incremental α values (0.0002, 0.012, and 0.038) in order to achieve an overall α =0.05.

There are four comparisons to warrant early stopping: (1) Clear superiority: Superiority of the intervention is sufficiently large that the study should be discontinued because equipoise is lost and randomization should no longer proceed. (2) Futility: The evidence in favor of the intervention is such that at the completion of the study, there is inadequate power to detect an improvement and the study should be dropped. (3) Inferiority: The evidence shows that the intervention is worse than the control and the study needs to be stopped. (4) Safety: Secondary safety outcomes that are considered serious adverse events possible related to the study are clinically higher in the intervention group. (See also section 4.4 for additional safety outcomes).

- (1) Clear superiority -- whether the experimental treatment is clearly inferior to standard therapy. For these calculations, we trade off the power to detect a difference and the size of that difference. Assuming α =0.0002 for boundaries for the initial interim analysis when 200 children have been followed to completion, power is limited except to detect large reductions in outcomes of death and BPD. For example, power is approximately 0.81 to detect a reduction from 65% in the conventional therapy to 32.5% in the experimental therapy, a 50% relative reduction. For the second interim analysis, using α =0.012, power with 400 children followed is about 0.85 to detect an absolute reduction from 65% to 40% in the risk of death plus BPD. Thus, early or premature stopping for superiority is unlikely, without dramatic improvement from experimental treatment.
- (2) Futility. Early stopping based on futility of the primary outcome will not be considered independently of the secondary clinical and safety outcomes. In the event that the intervention arm has equivalent BPD/death rates to the standard care arm, it would still be clinically useful to know if the intervention improves any of the secondary outcomes (that are closer to the time of the intervention) or decreases the serious adverse event rate.
- (3) Inferiority. Power is limited to identify inferiority of the experimental treatment, with 0.8 power to demonstrate a 15% point increase in the risk of outcome from 65% in the standard therapy to 80% in the intervention.

(4) Safety.

- (a) Early stopping based on inferior safety and non-inferior efficacy must be based largely on descriptive data and close examination of adverse events. With 200 subjects per group at a second early stopping review, and assuming that the experimental therapy is actually no worse than conventional care, observed risk in the experimental group would have to be at most 0.5 (risk of death and BPD) to have 80% power to show non-inferior efficacy (with alpha = 0.012).
- (b) To justify stopping for non-inferior efficacy and superior safety again will require a substantial observed improvement in the experimental arm at the second early stopping time.

In summary, given the projected number of patients to be enrolled, early stopping will be unlikely unless the observed effect of experimental care is clearly better or worse than standard care at the planned early stopping assessment times.

All of the standard reports described in the previous section will be provided to the DSMC with this analysis. Additional measures to be considered at the interim analysis include baseline clinical factors and adverse events. The study population for all of the analyses provided to the DSMC is the intent-to-treat population, including all participants and time points for which data have been entered and verified in the study database. A summary of the analyses to be included in the interim report is outlined below. Additional details of the statistical methods to be used are given in the next section regarding the final analysis.

4.1 Blinding

The study will be blinded in treatment allocation; patients, parents and clinicians will be unblinded once treatment is assigned; and then blinded analyses. All analyses provided to the DSMC will be provided by intervention, but with the individual interventions identified only as A and B. The same code will be used for each intervention throughout the report. A sealed envelope with the codes for these interventions will be provided to the chair of the DSMC, to allow the DSMC to unblind these results if needed for safety reasons. These codes are also maintained by a member of the DCC who is not involved in the group trials and are not made

available to any other DCC members, including the statisticians. None of the personnel in the DCC, including the statisticians, will have access to these codes until the study has been completed, all data are entered and verified in the database, and the DSMC has approved unblinding of the intervention results.

4.2 Baseline/Delivery Data

Selected baseline factors will be summarized and compared between intervention groups to evaluate the adequacy of randomization, the impact of any post-randomization dropout, and to identify any imbalances that may affect intervention comparisons (Appendix B, Table 1 and Table 2). Standard descriptive statistics will be used to describe baseline characteristics, both overall and within each intervention group. Baseline characteristics examined will include maternal and gestational age, race/ethnicity, Clinical Site, consenting procedure (antenatal vs. deferred consent), route of treatment (facemask vs. nasopharyngeal tube), and enrollment date (in 3 month increments). Baseline values of selected secondary outcomes will be included as part of that analysis (see below).

Summary statistics such as medians, ranges, minima and maxima, and percentages will be produced for all measured variables. Frequencies will be computed for all categorical and ordinal variables. Graphical methods including stem and leaf plots, histograms, scatterplots, and boxplots, will be used in order to understand aspects of data quality, examine assumptions (such as normality) underlying statistical models, identify potential influential points, and guide in the choice of transformations if warranted. The balance of baseline measures across the intervention groups will be compared by inspection and by standardized differences. Overall imbalance across several or all covariates will be examined using multivariable logistic regression with treatment assignment as the outcome.

